## ABSTRACT

**Background:** Obesity is a chronic disease and is an established risk factor for other chronic diseases and mortality. Young adulthood is a period when people may be highly amenable to healthy behaviour change, develop lifelong healthy behaviours, and when primary prevention of obesity may be most feasible. Interventions in early adulthood have the potential for primary or primordial prevention (i.e., preventing risk factors before disease onset). The primary objective of this study is to determine the feasibility of a 6-month behavioural and educational intervention to promote healthy behaviours for obesity prevention among young adults.

**Methods:** This is the study protocol for a pilot randomized controlled trial. Young adults (age 18-29) attending McMaster University, Hamilton, Canada, will be recruited and randomized to either the intervention or control. The intervention will include individual motivational interviewing sessions (online or in-person) with a trained interviewer plus educational materials (based on Canada's food guide and physical activity recommendations). The control group will receive educational materials only. The primary feasibility outcomes that will be evaluated as part of this pilot study include enrollment, retention ( $\geq 80\%$ ), data completion ( $\geq 80\%$  of weights measured, and surveys completed), and participant satisfaction. Secondary clinical outcomes will include body mass index (BMI) change from baseline to 6-months, physical activity, nutrition risk, health-related quality of life mental health and economic outcomes. Outcomes will be measured remotely using 'smart' electronic scales, activity trackers, and online questionnaires at baseline and every 2 months. Risk stratification will be applied at baseline to identify participants at high risk of obesity (e.g., due to family or personal history). Exit questionnaires will collect data on how participants felt about the study and cost analysis will be conducted.

**Discussion:** Our pilot randomized controlled trial will evaluate the feasibility of an obesity prevention intervention in early adulthood and will inform future larger studies for obesity prevention. The results of this

study have the potential to directly contribute to the primary prevention of several types of cancer by testing an intervention that could be scalable to public health, post-secondary education, or primary care settings.

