### ***Measurement of Outcomes***

Table 1 describes all outcomes. The primary feasibility outcomes that will be measured are recruitment, retention, data completion, and participant satisfaction. We will consider a larger trial feasible if recruitment rates are  $\geq 50\%$ , retention rates are  $\geq 80\%$ , and the data completion rate for all secondary clinical outcomes is  $\geq 80\%$ . Participant satisfaction with different aspects of the study will be measured at the exit questionnaire using a Likert scale and semi-structured qualitative free-text responses.

Secondary outcomes will include BMI change from baseline to 6-months. Interventions are more successful if longer than 4 months in duration.(36) All study participants will have one in-person visit with the research assistant at the start of the study where baseline weight and height will be measured using standardized methods with calibrated study instruments. Participants (both intervention and control) will then receive a Fitbit activity tracker to wear for the duration of the study. Study participants will be asked to visit the

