study office once a month to conduct a self weigh-in using a Fitbit electronic ‘smart’ scale (e-scale). They will be asked to weigh themselves monthly and reminders will be sent by email or text message. E-scales are feasible and valid for research conducted remotely and participant adherence to home weigh-ins is high(37–39), as part of this feasibility study we will assess the adherence to self weigh-ins when the scale is located in a private study office. Other secondary outcomes will include nutrition risk, physical activity (measured as 24-hour movement, including sedentary time and sleep), and mental health collected using online questionnaires at baseline and every 2 months. Nutrition risk will be measured using the National Cancer Institute's Dietary Screener Questionnaire (DSQ). The DSQ measures the frequency of intake of selected foods that are known to affect risk of cancer and obesity, including fruits, vegetables, whole grains, and sugary drinks. The DSQ has good validity compared to 24-hour recalls.(40) Self-reported physical activity, sedentary time, recreational screen time and sleep will be measured to describe adherence to recommended 24-hour movement guidelines using questionnaires previously used in young adults(41), including the International Physical Activity Questionnaire (IPAQ)(42), and International Sedentary Assessment Tool (ISAT).(43) The Insomnia Severity Index will also be included as a measure of perceived sleep quality.(44) Mental health is an important upstream determinant of health behaviours and is highly associated with obesity risk. We will measure depressive symptoms, anxiety and health-related quality of Life using the following validated tools: Centre for Epidemiologic Studies Depression Measure -10 (CESD-10)(45), Generalized Anxiety Disorder -7 (GAD-7)(46), and Euroqol-5D-5L (EQ-5D-5L).(47) We anticipate that some youth may also raise issues related to alcohol or substance use in the interviews, thus we have included questions that ask about alcohol, smoking, cannabis and medication use in the questionnaires. A single-item measure of body satisfaction is included in the study to evaluate any changes over the course of the study.(48) A validated two-item food insecurity screen is also included.(49)

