#### ***Data collection and management***

All data will be stored in a secure REDCap database. Surveys will be collected online using secure electronic data capture in REDcap. The final trial dataset will only be available to select members of the research team (LA, LM, TI). The final dataset will not be made publicly available to protect the confidentiality of participants, but de-identified data could be made available upon request. Baseline surveys will collect detailed data on socioeconomic variables, including age, sex, gender identity, income, and food security, medical history, and the secondary outcomes described above (nutrition, physical activity, sedentary time, mental health). Follow-up surveys administered every 2 months (at 2, 4 and 6 months) will collect updated data on secondary outcomes. Participants in both the control and intervention groups will receive a \$30 gift card at the time of each survey completion. We will continue to collect data from participants if they deviate from protocol unless there is withdrawal from the study. To ensure confidentiality, a unique study id number will be used for the weight and activity data and linked at McMaster by the research team to the main study database.

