### ***Sample size***

Our sample size estimation was based on feasibility considerations and calculated using WINPEPI.(53) Using a 95% confidence level, assuming that 80% of the participants will complete the study with a 7.5% margin of error, 110 participants are needed (55 intervention and 55 control). This sample size is not sufficiently powered to make between-group comparisons but will provide accurate data on feasibility and estimates of effect size variability that will inform the sample size calculation of a larger definitive trial.

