**Table 1. Summary of all outcome measures and method of analysis**

Outcome measure	Variable Type	Measurement	Method of analysis
Primary Feasibility Outcomes			
Recruitment rate	Binary	% of eligible participants who are recruited from all those who contact the research team to learn about the study	Feasibility threshold of ≥50%

Retention rate	Binary	% of participants who complete 6-month follow-up	Feasibility threshold of $\geq 80\%$ .
Data completion	Binary	% of secondary outcomes with no missing data	Feasibility threshold of $\geq 80\%$ .
Satisfaction	Continuous	Mean score on a 7-point Likert scale	Mean satisfaction score $\geq 4$
Secondary Outcomes			
BMI change	Continuous	Change in BMI from baseline to 6-month follow-up, weight measures using wifi enabled smart scales	Mean, SD
Physical activity	Binary	International Physical Activity Questionnaire (IPAQ)	Mean, SD
	Continuous	Minutes per day from activity trackers	Mean, SD
Sedentary time	Binary	International Sedentary Assessment Tool (ISAT)	Mean, SD
Nutrition	Continuous	National Cancer Institute's Dietary Screener Questionnaire (DSQ)	Mean, SD
Mental health	Binary	Depressive symptoms (CESD-10) score $>10$ , Anxiety (GAD-7) score $>10$ ,	N, %
Health-related quality of life	Continuous	Quality of Life (EQ-5D-5L)	Median, IQR

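### Data completion, a primary feasibility outcome with an 80% mark, is defined inconsistently in the abstract, the methods text and Table 1, and the Table 1 wording cannot work as a pass mark if read literally

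*Combined protocol and SAP*

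**What the plan says.** All of the following is in the Combined protocol and SAP.

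- **Abstract:** data completion is at least 80% "of weights measured, and surveys completed". The next sentences list the measurement methods as smart scales, "activity trackers, and online questionnaires at baseline and every 2 months".
- **Measurement of Outcomes:** a larger trial is considered feasible if, among other conditions, "the data completion rate for all secondary clinical outcomes is" at least 80%. No unit, denominator or time point follows. On trackers, participants in both arms "receive a Fitbit activity tracker to wear for the duration of the study". On weights: "They will be asked to weigh themselves monthly and reminders will be sent by email or text message".
- **Data collection and management:** "Follow-up surveys administered every 2 months (at 2, 4 and 6 months) will collect updated data on secondary outcomes".
- **Table 1:** data completion is typed as binary and measured as the percentage "of secondary outcomes with no missing data", with a threshold of 80%. The secondary outcomes in the same table include BMI change to 6 months, the questionnaire measures and tracker minutes per day.
- **Sample size:** N = 110 is derived by "assuming that 80% of the participants will complete the study with a 7.5% margin of error". That figure concerns study completion, not data completion.
- **Reporting and interpretation:** each feasibility outcome is to be reported as meeting its threshold or not, with a traffic-light colour that informs progression. Only one green is required.

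**The concern.** The three wordings differ in unit and in scope. The abstract counts weigh-ins and surveys. Table 1 counts outcomes, and one of those outcomes (tracker minutes) comes from neither a weigh-in nor a survey. The methods text fixes the scope only. No section says whether the denominator is everyone randomised or those retained, whether baseline counts, whether one time point or all are needed, or how a partly completed survey is treated.

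Feasibility is the primary objective and the secondary outcomes get no formal testing, so the met/not-met statements on the feasibility thresholds are the trial's main results. If the definition is open, the same data can be reported as meeting or missing the 80% mark, and the choice could be made after the data are seen.

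**Working it through.** **1. The plan's own figure.** Single-proportion precision at 95% confidence: 1.96² × 0.80 × 0.20 / 0.075² = 109.27, rounded up to 110. The stated N reproduces and is not in dispute. The 80% mark on 110 participants is 88.

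**2. Table 1 read literally.** An outcome counts only if no participant has a missing value. If each participant has the 6-month value with probability q, independently, the chance that an outcome is fully observed is q^110:

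| q | q^110 |
|---|---|
| 0.80 (the planned completion) | 2.2 × 10⁻¹¹ |
| 0.95 | 0.0035 |
| 0.99 | 0.33 |

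To expect 80% of outcomes to qualify, q must be 0.80^(1/110) = 0.998. The wording cannot serve as a pass mark in a trial that plans for 80% completion.

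**3. Two workable readings compared.** One divides observed by scheduled data points. The other takes the share of randomised participants with complete data. For simplicity the illustration uses surveys only, at 2, 4 and 6 months and without baseline. Its assumptions, none of them in the plan, are that dropout is spread evenly over 6 months and that each scheduled survey is obtained with probability 0.95 while the participant is in the study.

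Expected rates with 20% loss:
- In study at 2, 4 and 6 months: 0.933, 0.867, 0.800; mean 0.867.
- Data-point rate: 0.867 × 0.95 = 0.823, above the mark.
- Participants with the 6-month survey: 0.80 × 0.95 = 0.760, below it.
- Participants with all three surveys, misses independent: 0.80 × 0.95³ = 0.686, below it.

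Simulated share of trials (20,000 trials, n = 110) in which the data-point count passes and the participant count fails:

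| Scenario | Misses clustered by participant | Independent, 6-month survey only | Independent, all three surveys |
|---|---|---|---|
| 20% linear loss | 59% | 61% | 80% |
| Same, and retention also met | 34% | 35% | 54% |
| 15% linear loss | 33% | 34% | 93% |
| 10% linear loss | 4% | 4% | 72% |
| 20% lost straight after baseline | 0% | 2% | 15% |

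With no missing data beyond dropout, the participant count merely repeats the retention outcome.

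**4. Effect of counting baseline.** The abstract does not exclude baseline. If baseline surveys are counted in the data-point rate, the 20% linear-loss row becomes 80%, 81% and 99%. With loss straight after baseline, the clustered case moves from 0% to 57%.

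The rate itself changes as follows:
- Linear loss, surveys: (1 + 3 × 0.823)/4 = 0.868 with baseline, 0.823 without; 4.4 points.
- Linear loss, weights: in-study mean over months 1 to 6 is 0.883, × 0.95 = 0.839; with baseline (1 + 6 × 0.839)/7 = 0.862; 2.3 points.
- Loss straight after baseline: 0.80 × 0.95 = 0.760 without baseline, against 0.820 for surveys and 0.794 for weights with it; 6.0 and 3.4 points.

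**The case against.** The strongest reply is that this is loose wording, not a risk to the result. Table 1 types data completion as binary, as it does retention, which suggests a complete/incomplete flag summarised as a rate. No analyst would apply a rule that one dropout defeats. An abstract may abbreviate, the 80% mark is the same everywhere, and weights and surveys feed every secondary outcome except tracker minutes.

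Much of this stands. A reader might infer from step 2 that the trial will report a completion rate near zero. The documents do not support that; what follows is that some unwritten definition will have to be used. But the abstract has no full definition to abbreviate, since neither Table 1 nor the methods text supplies one.

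The objection to the simulation also stands. Both arms are survey-only stand-ins, so a reader should not take the percentages as properties of the abstract's or Table 1's definition. The leading scenario sits on the threshold, where retention itself fails in about 44% of trials, and the results range from 0% to 93% with the assumptions. They show that opposite verdicts are possible, not how likely they are in this trial.

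Finally, a reader might infer that the definition decides whether a larger trial goes ahead. Reporting and interpretation does not say so: colours inform progression, yellow allows modification, and one green is enough.

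**Conclusion.** The inconsistency is real and should be fixed. It rests on the text alone: different units, different scope for tracker data, and no counting rule in any section. That the literal Table 1 rule is unusable follows from the planned 80% completion and N = 110.

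How often the choice would change the reported result depends on assumptions outside the plan. Near 80% retention, with 95% in-study completion and linear loss, it is common (59% to 80% of trials, 34% to 54% with retention also met). At 90% retention it is rare (about 4%) unless all three surveys are required and misses are independent (72%). The consequence is confined to the reported verdict and colour for one of four primary feasibility outcomes. The sample size is unaffected.

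The documents do not establish that tracker data must count toward the mark. Table 1 points one way and the abstract the other, so that choice belongs to the sponsor.

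**What to change.** Replace the Table 1 wording and align the abstract and Measurement of Outcomes with one definition: observed divided by scheduled post-baseline data points, over all randomised participants, before any imputation. Calculate it separately for weights (monthly) and surveys (2, 4 and 6 months), and compare each rate with 80%.

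Report tracker completeness alongside. The sponsor should state in advance whether it counts toward the 80% mark, and what makes a tracker record or a partly completed survey valid. Report the per-participant rate at 6 months as a supporting figure.

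The cost is wording in three places and two short validity rules, with no extra data collection. The downside is a less favourable figure: leaving out baseline lowers the rate by roughly 2 to 6 points in the scenarios above.

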### ***Consent and Ethics***

Ethics approval was obtained from the Hamilton Integrated Research Ethics Board on July 25, 2022 (HiREB Project Number: 14675). Informed consent will be obtained from all participants at the first in-person visit. Participants may choose to withdraw from the study at any time and when possible, we will capture the reasons for withdrawal. Consideration has been given to issues of equity (advertisement and recruitment materials, research staff and investigators) and among this population of students, we do not anticipate that the English-language requirement will be a barrier.

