### ***Reporting and interpretation***

Study results will be reported following the CONSORT extension for randomized pilot and feasibility trials guideline(54) For each feasibility outcome, we will report whether the feasibility threshold was met and use a traffic light system to inform progression to a larger trial. Green: proceed to larger trial; yellow: proceed with some modifications; red: larger trial not feasible. At least one feasibility outcome must be green. Any deviations to the protocol will be recorded and reported in the final manuscript. Study results will be shared with participants through a final report and published in a peer-reviewed manuscript.

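### The progression rules conflict: satisfaction is outside the three-threshold go rule, yet as a midpoint score it could be the only green outcome under the traffic-light sentence

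*Combined protocol and SAP*

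**What the plan says.** Three places in the combined protocol and SAP bear on whether the pilot supports a larger trial.

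- **Measurement of Outcomes** names four feasibility outcomes but builds its go rule from three. It begins "We will consider a larger trial feasible if recruitment rates are" at least 50%, and continues with retention of at least 80% and completion of the secondary clinical outcomes of at least 80%. Satisfaction is described separately: "Participant satisfaction with different aspects of the study will be measured at the exit questionnaire", by Likert scale and "semi-structured qualitative free-text responses". No satisfaction threshold appears there.
- **Table 1** lists satisfaction among the primary feasibility outcomes, as "Mean score on a 7-point Likert scale", with a threshold of a mean of 4 or more. It gives no anchors, no numeric coding, no rule for combining the different aspects rated, and no statement of whether the mean is taken over both arms or by arm.
- **Reporting and interpretation** applies a traffic light to each feasibility outcome: "Green: proceed to larger trial; yellow: proceed with some modifications; red: larger trial not feasible". No numeric limits for yellow or red are given for any outcome. The only statement on how many outcomes must reach a given colour is "At least one feasibility outcome must be green".

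For participants who leave, Consent and Ethics says that "when possible, we will capture the reasons for withdrawal". It mentions no satisfaction score for them.

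**The concern.** A pilot's main product is its go/no-go decision, so the rule should give one answer for any set of results. Here a reader could apply the three-threshold rule, in which satisfaction plays no part, or the traffic-light sentence, in which satisfaction counts equally with the other three and one green meets the stated minimum.

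The satisfaction threshold makes this matter more. Under the usual 1 to 7 coding, a mean of 4 is the centre of the scale, and because the rule is 4 or more, a group in which everyone chose the middle option would meet it. If recruitment, retention and completion all missed, a neutral satisfaction score could still supply the one green that Reporting and interpretation asks for. A report could then present progression as consistent with the plan although Measurement of Outcomes would not call the larger trial feasible.

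**Working it through.** **Inputs.** Thresholds of 50%, 80% and 80%, and a mean of 4 (Measurement of Outcomes; Table 1). A minimum of one green (Reporting and interpretation). Sample size 110, 55 per arm, 80% completion, margin 7.5%, 95% confidence (Sample size). Assumed, because the documents do not say: scale coding, standard deviation of satisfaction, who answers at exit, and that green means the stated threshold is met.

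**1. The plan's own figure.** n = 1.96² × 0.80 × 0.20 / 0.075² = 109.27, rounded up to 110. It reproduces. The point does not rest on it; it supplies only the expected number of completers, 0.80 × 110 = 88.

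**2. The two rules side by side.** Score each of the four outcomes as met or missed: 2⁴ = 16 patterns.

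- Three-threshold rule, read as complete: go in 2 patterns (the three met, satisfaction either way).
- One-green sentence, read as complete: go in 16 − 1 = 15 patterns.
- The readings disagree in 15 − 2 = 13 patterns. In one of these, satisfaction is the only outcome met.

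To illustrate the gap in probability, suppose the four outcomes are independent and each is met with probability q (both assumed). Then P(at least one of four) = 1 − (1 − q)⁴ and P(all three named) = q³.

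| q | At least one of four | All three named |
|---|---|---|
| 0.3 | 0.76 | 0.03 |
| 0.5 | 0.94 | 0.125 |
| 0.7 | 0.99 | 0.34 |

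**3. Where 4 lies on the scale.** Midpoint = (lowest + highest)/2. Coded 1 to 7: (1 + 7)/2 = 4, equal to the threshold. Coded 0 to 6: (0 + 6)/2 = 3, and the threshold is above it.

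**4. What the threshold separates.** With 88 respondents and true mean μ, P(pass) = 1 − Φ((4 − μ)/(SD/√88)).

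| True mean | SD 1 | SD 1.5 | SD 2 |
|---|---|---|---|
| 3.75 | 0.01 | 0.06 | 0.12 |
| 4.00 | 0.50 | 0.50 | 0.50 |
| 4.25 | 0.99 | 0.94 | 0.88 |

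An exact calculation for scores spread evenly over 1 to 7 gives 0.511 at a cut of 4 or more. By symmetry, a cut strictly above 4 gives 1 − 0.511 = 0.489. An illustrative cut of 4.5 gives 0.010. If every respondent scores 4, the present rule is met with certainty.

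**5. Exit-only measurement.** Suppose only the 80% who complete respond, with mean 4.0, and the other 20% would have averaged 1, 2 or 3 (all assumed). The mean over all randomised is 0.8 × 4.0 + 0.2 × 1 = 3.4, and likewise 3.6 or 3.8, while the criterion is still met. With a completers' mean of 4.3, the overall mean falls below 4 only if the others average under (4 − 0.8 × 4.3)/0.2 = 2.8.

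**The case against.** The strongest reply is that Reporting and interpretation states a necessary condition. Saying that one outcome must be green does not say that one green is enough, and the same section has a red category meaning that a larger trial is not feasible. The three-threshold rule excludes satisfaction, so under it satisfaction cannot carry progression. This stands. A reader might infer that the plan lets a single green outcome suffice; the text does not say so. What remains is that neither section refers to the other, no colour bands are defined, and nothing says how a green on one outcome combines with a red on another.

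Other inferences also go further than the documents:

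- *Indifferent participants pass.* This is certain only if the observed mean is exactly 4 or above, as when all answer 4. A neutral group with varying scores passes about half the time. Any point threshold behaves this way when the truth lies on it, including 80% retention, so the 50% figure is not a fault particular to satisfaction.
- *Half the scores say nothing about the counselling.* Pooling of arms is not stated, and since several aspects of the study are rated, counselling may have its own item.
- *Only completers are scored.* This is likely but not stated. Retention has its own threshold, free text accompanies the score, and Data collection and management keeps collecting data from participants who deviate from protocol unless they withdraw.
- *Satisfaction is the easiest criterion.* The documents give no expected satisfaction distribution from which to judge this.

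**Conclusion.** The point holds as a conflict between progression rules, made worse by an undefined satisfaction scale. Read as complete rules, the two statements give different decisions in 13 of 16 met-or-missed patterns. One of these is the case in which a midpoint satisfaction score is the sole green and the other three outcomes miss. The count treats green as the Table 1 threshold being met. The midpoint description rests on 1 to 7 coding and would not apply under 0 to 6.

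The documents do not establish that the plan would in fact progress on satisfaction alone; they fail to exclude it in the one sentence that states how many outcomes must be green. The exit-only and pass-probability figures are illustrations under assumed inputs. They support stating the scale, the respondents and the cut; they do not show bias.

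**What to change.** 1. Amend Reporting and interpretation so that progression requires the three thresholds in Measurement of Outcomes. Possible wording: *Progression requires recruitment of at least 50%, retention of at least 80% and data completion of at least 80%. Satisfaction is graded and reported alongside; a green on satisfaction alone does not meet the progression rule.*
2. Align Table 1 with that text, so that satisfaction's role is the same in all three places, and give numeric yellow and red limits so that the colours can be applied.
3. State the satisfaction coding and anchors and how the aspects are combined. Set green above the neutral point, with a mean of exactly neutral at most yellow, and justify the cut. Replacing 4 or more by strictly above 4 removes the all-neutral pass but barely alters the chance for a varied neutral group (0.511 to 0.489), so the distance above neutral deserves a sentence.
4. Report satisfaction by arm, with respondents over randomised.

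The cost is wording and one extra reporting line, with no change in sample size or data collection. The small downside is that the go decision becomes harder to reach.

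Three further steps are optional. A lower 95% confidence limit above 4 would, with 44 respondents (0.80 × 55) and an assumed SD of 1.5, need a mean of about 4 + 1.96 × 1.5/√44 = 4.44, and it would treat satisfaction differently from the other point thresholds. Restricting the criterion to the intervention arm would drop controls' views on trackers, weigh-ins and surveys. Surveying withdrawn participants departs from the plan's rule that collection stops at withdrawal and may need a consent or ethics change.

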**The primary study objective is:**

1) To determine the feasibility (enrollment, retention, data completion, satisfaction) of a 6-month behavioural and educational intervention to promote healthy behaviours for obesity prevention among young adults.

The **secondary objectives are:**

2) To determine the effects of the 6-month behavioural and educational intervention, compared to an educational intervention only, on change in BMI, health behaviours (nutrition, physical activity and sedentary time), health-related quality of life, and mental health (depression and anxiety).

3) To explore whether obesity risk stratification tools identify young adults who may be more successful in an obesity intervention.

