### ***Data Analysis***

The analysis and reporting of our results will be done according to the CONSORT guidelines.(51) The data analyst will be blinded. Patient screening, randomization, allocation, and follow-up numbers will be illustrated in a flow diagram. Baseline data will be reported in a table for both groups (Intervention and Control) and summarised as means (standard deviation) or median (first quartile, third quartile) for continuous variables and counts (percent) for categorical variables. Data on feasibility outcomes will be measured and compared to pre-determined thresholds for interpretation. The primary analysis will be by intention-to-treat (data from participants will be analyzed according to their allocation irrespective of whether they received that intervention). For these purposes, a complete data set is required. Multiple imputation techniques will be used to manage missing data points. Comparison of groups for secondary outcomes will be reported descriptively for this pilot study. No formal significance testing for comparisons of the secondary clinical outcomes will be made because this is a pilot study with *a priori* sample size determined based on feasibility outcomes only. It is well established that there are sex and gender differences in obesity.(52) Disaggregated data on sex and gender will be reported.

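### Depression and anxiety are planned to be reported only as the share above a cut-off, so no follow-up or change-score mean or SD is pre-specified for either scale

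*Combined protocol and SAP*

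**What the plan says.** Table 1 gives mental health one row among the secondary outcomes. Its variable type is binary, it is defined by "Depressive symptoms (CESD-10) score" above 10 and a GAD-7 score above 10, and its method of analysis is number and percent. In the same table BMI change, activity-tracker minutes and the dietary screener are continuous with mean and SD, and EQ-5D-5L is continuous with median and IQR.

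The whole instruments are administered. Measurement of Outcomes states: "We will measure depressive symptoms, anxiety and health-related quality of Life using the following validated tools", and then lists CESD-10, GAD-7 and EQ-5D-5L. Data collection and management puts mental health in the baseline survey and has secondary outcomes updated at 2, 4 and 6 months.

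Three other statements bear on the point:
- The secondary objectives include the effect of the intervention on "health-related quality of life, and mental health (depression and anxiety").
- The Sample size section says the pilot will supply "estimates of effect size variability that will inform the sample size calculation of a larger definitive trial".
- Data Analysis says "No formal significance testing for comparisons of the secondary clinical outcomes will be made". It also says that baseline data will be "summarised as means (standard deviation) or median (first quartile, third quartile) for continuous variables", without saying whether the two mental health scores are among them.

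**The concern.** A participant whose CESD-10 or GAD-7 score moves a good deal without crossing 10 counts as unchanged in a number-and-percent summary, and one who moves a single point across it counts as fully changed. For an objective about effects on depression and anxiety, that is the less informative of two summaries available from the same data. The BMI row specifies change from baseline. The mental health row does not, and no reason is given for treating these scores differently from the dietary and quality-of-life scores.

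The second issue is planning. A larger trial that used either score as a continuous endpoint would need its SD, ideally for the change or the follow-up value. The plan promises variability estimates in general terms but names none for these scales. If the summary is chosen only after the data are seen, the choice between score and cut-off also becomes post hoc.

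**Working it through.** **1. The plan's own figure.** The only sample size figure is 110, from a 95% confidence level, 80% completion and a 7.5-point margin (Sample size):

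n = 1.96² × 0.80 × 0.20 / 0.075² = 109.27, rounded up to 110.

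The half-width at 110 is 1.96 × √(0.16/110) = 7.48 points. The figure reproduces, and no mental health input enters it.

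**2. Information kept by the cut-off.** The documents state neither a distribution for the scores nor a share above 10. I assume a normal score and vary the share p. The efficiency of the dichotomised score relative to the score itself, for a small shift between arms, is

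E = φ(z)² / [p(1 − p)], where z is the normal quantile with upper tail p.

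| Share above cut-off (assumed) | E | Loss |
|---|---|---|
| 50% | 0.637 | 36% |
| 40% | 0.622 | 38% |
| 30% | 0.576 | 42% |
| 20% | 0.490 | 51% |
| 10% | 0.342 | 66% |

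The loss is smallest, 36%, when the cut-off falls at the median. A loss of 40% to 50% needs a share of about 34% down to 21%.

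**3. Cross-check by sample size.** Take a 0.3 SD reduction, two-sided 5% level and 80% power.
- Score: n per arm = 2(1.96 + 0.8416)² / 0.3² = 174.4, so 175.
- Cut-off: n per arm = [1.96√(2p̄(1 − p̄)) + 0.8416√(p₁(1 − p₁) + p₂(1 − p₂))]² / (p₁ − p₂)², where p₂ is the upper tail beyond z + 0.3 and p̄ is the mean of p₁ and p₂.

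For control shares of 50%, 40%, 30%, 20% and 10% this gives 278, 293, 327, 400 and 609 per arm. The corresponding losses, 1 − 175/n, are 37%, 40%, 46%, 56% and 71%. They are slightly larger than in step 2 because the shift is not small.

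**4. Precision in this pilot.** With 55 per arm, the 95% half-width for a difference in proportions is 1.96 × √(2p(1 − p)/55), which is 15.0 points at p = 0.20 and 18.3 at p = 0.40. At the assumed 80% completion (0.80 × 55 = 44 per arm) these become 16.7 and 20.5.

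To compare with the score, divide by φ(z), since a shift of δ SD moves the proportion by about φ(z)δ. With 55 per arm the cut-off gives 0.150/0.280 = 0.53 SD and 0.183/0.386 = 0.47 SD. The score gives 1.96 × √(2/55) = 0.37 SD. The interval is therefore about 1.4 and 1.3 times as wide, matching 1/√0.490 and 1/√0.622.

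**5. Value of an SD from this pilot.** The 95% limits for an SD are the estimate times √[(n − 1)/χ²] at the 97.5% and 2.5% points. With 55 per arm the multipliers are 0.84 and 1.23, and with 44 they are 0.83 and 1.27. An SD reported by arm would be a usable planning input.

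**The case against.** The strongest reply is that nothing in the pilot turns on this. Secondary comparisons are descriptive, the plan disclaims power for between-group comparisons, and progression depends on recruitment, retention, completion and satisfaction. The share above a cut-off is a recognised descriptive summary. All of that stands, and it limits the point to an improvement in reporting.

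A reader might also infer several stronger things that the documents do not support.
- That the plan throws away 40% to 50% of the information. That figure requires a particular prevalence and a normal score, and the plan states neither. The two scales may also have different prevalences.
- That no SD will exist. The full scores are collected and kept, so one can be computed later, and the baseline summaries in Data Analysis may already include it.
- That the pilot cannot inform mental health planning. If the larger trial kept the binary outcome, the proportion would be what it needs, and the plan supplies it. The gap arises only for a continuous mental health endpoint, which the documents do not announce.
- That harm would be missed. Safety protocols and unanticipated outcomes refers generally to mental health concerns, including eating disorders, and handles them by individual assessment and referral, not by comparing group scores.

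Finally, Table 1 does not list everything collected: the Insomnia Severity Index and the body satisfaction item are absent. A missing row is therefore not proof that the scores will go unreported. What remains is that, for these two scales, Table 1 does name a method, it is number and percent, and no section adds a continuous outcome summary.

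**Conclusion.** The point holds as a gap in pre-specified outcome reporting. For CESD-10 and GAD-7 the plan specifies only the share above 10, so no follow-up or change-score mean or SD is committed to, although the scores are collected four times and variability estimates are a stated purpose of the pilot.

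Under a roughly normal score the loss is at least 36% whatever the cut-off. It is 38% to 51% if 20% to 40% exceed it, and larger if fewer do. The prevalence range is assumed, and a markedly skewed score would give different figures. The direction of the planning argument depends on the larger trial using a continuous mental health endpoint. N = 110, the feasibility thresholds, the progression rule and planning on BMI are all untouched. This is a minor point, worth making because the remedy is free.

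**What to change.** In the mental health row of Table 1, add the continuous CESD-10 and GAD-7 scores, each summarised by arm as mean, SD and change from baseline, with a descriptive 95% confidence interval for the difference between arms and no significance test. Keep number and percent above the cut-off alongside. An interval is compatible with Data Analysis, which rules out significance testing of secondary outcomes but not interval estimates.

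The cost is an extra table line per scale. No new data, visits or participants are needed, and the sample size does not change.
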